## 1.0 Background and Rationale

With the introduction of effective antiretroviral therapy (ART), HIV-infected persons can now survive for decades, but this success has been accompanied by an increased risk of developing metabolic disease compared HIV-negative persons. In the Multicenter AIDS Cohort Study, HIV-infected men had a greater than 4-fold increased incidence of a new diabetes diagnosis compared to HIV-negative men after adjusting for age and body mass index (BMI). Prevalence studies of diabetes in HIV-infected individuals on ART have reported incidence rates of 3.1 to 14 per 1000 patient-years. Furthermore, treated HIV infection appears to act synergistically with other risk factors, and diabetes prevalence is especially high among HIV-infected individuals with obesity and advanced age.

While early studies found inflammation (i.e., innate immune activation) was associated with diabetes risk in persons with HIV, more recent data suggest chronic cellular immune activation may have a central role in diabetes pathogenesis. Recent studies from HIV-negative subjects identified several associations between adaptive immune cell populations and impaired glucose tolerance. Peripheral T regulatory ( $T_{reg}$ ) cells are significantly lower in patients with type-2 diabetes and inversely proportional to HbA1c levels, while the numbers of CD25+ (activated) T cells and the proportion of  $T_{H1}$  (pro-inflammatory) cells are higher in diabetics. More recently, an analysis of the Multi-Ethnic Study of Atherosclerosis (MESA) cohort found a higher proportion of circulating memory CD4+ T cells and  $T_{H1}$  cells was associated with insulin levels and prevalent type 2 diabetes. Our group found a similar association between memory CD4+ T cells and incident diabetes for HIV patients in the Veterans Aging Cohort Study (VACS; see preliminary data).

T cells and macrophages are present in the stromal fraction of adipose tissue and affect adipocyte function. The striking increase in adipose tissue CD4+  $T_{H1}$  cells and CD8+ T cells, and a decrease in  $T_{reg}$  cells, observed in obesity may have an important role in the development of insulin resistance. Secretion of the proinflammatory cytokines IFN- $\gamma$  and IL-17 by  $T_{H1}$  and  $T_{H17}$  cells are implicated in the induction of proinflammatory M1 macrophages, which express IL-6 and tumor necrosis factor alpha (TNF- $\alpha$ ) and inhibit adipocyte insulin signaling by promoting phosphorylation of insulin receptor substrate 1. T cell infiltration into adipose tissue appears to be an early and necessary step preceding macrophage recruitment into adipose tissue, and in murine models antibody-induced CD8+ T cell depletion resulted in reduced M1 macrophage infiltration.

HIV offers a unique model to study linkages between peripheral T cells, adipose-resident T cells, adipose tissue function, and glucose tolerance. The changes in peripheral T cell subsets observed in chronic HIV-related immune activation are similar to those associated with insulin resistance in obese HIV-negative individuals. Immune cells translocate from the peripheral circulation into adipose tissue in a dynamic process, and we hypothesize that the chronic, HIV-related activation of peripheral CD4+ and CD8+ T cells may be accompanied by the accumulation of activated T cells in adipose tissue with adverse effects on metabolic activity. In this study, we will test the hypothesis that the oligoclonal expansion of chronically activated peripheral T cells in adipose tissue is a primary driver of macrophage inflammation and reduced adipocyte insulin sensitivity. Furthermore, we propose that this represents a central mechanistic linkage underlying the association between circulating T cell activation and incident diabetes risk observed in HIV-infected and HIV-negative individuals.

## 2.0 Preliminary Studies

**2.1. Adipose tissue from HIV+ persons is enriched for activated CD8+ T cells and there is a correlation between the percentage of circulating and adipose-resident memory CD4+ T cells:** To assess the relationships between circulating and adipose tissue T cell subset distributions, we conducted pilot study to compare T cell populations in adipose tissue biopsies and peripheral blood in 10 HIV infected subjects on long-term ART with sustained viral suppression. We collected 5-10 ml of abdominal subcutaneous adipose tissue using a 2.7 mm liposuction cannula. All subjects were fasting. Adipose tissue biopsies were repeatedly washed to eliminate any blood contamination and T cells extracted. Flow cytometry was performed on the adipose tissue T cells in addition to paired peripheral blood samples to measure CD3, CD4, and CD8 surface marker expression, and markers of activation (CD38, HLA-DR, CD69), senescence (CD57, PD-1), and memory cells (CD45RO).

We found adipose tissue to be enriched for activated CD8+ T cells (CD38+ and HLA-DR+) compared to blood – a cell type shown to promote adipose-resident macrophage activation in animal studies (**Table 1**). Furthermore, the relative percentages of CD4+ and CD8+ T cells were highly correlated between blood and adipose tissue, as were the percentages of activated (DR+) CD8+ T cells and memory (CD45RO+) CD4+ T cells. This finding supports our hypothesis that the distribution of T cell subsets in blood reflects the distribution of these T cell subsets in adipose tissue.

**Table 1. Pilot study comparing T cell subsets in blood and adipose tissue from HIV+ patients with long-term (>4 years) ART treatment and viral suppression (n=10)**

T cell subset	Comparison of median values in blood vs. adipose tissue			Correlation between blood and adipose tissue	
	Median in blood	Median in adipose tissue	p-value	Spearman rho	p-value
CD4+ %*	43.2	34.0	0.06	0.95	<0.01
CD4+ PD1+%	24.6	24.8	0.93	0.42	0.27
CD4+ CD57+%	2.2	5.4	0.06	0.95	<0.01
CD4+ CD38+%	4.0	2.4	0.44	0.16	0.68
CD4+ DR+%	1.0	2.5	0.001	0.52	0.15
CD4+ CD69+%	0.25	0.80	0.08	0.23	0.56
CD4+ CD45RO+%	50.3	57.4	0.86	0.83	0.005
CD8+ %*	50.4	60.9	0.11	0.85	0.004
CD8+ PD1+%	22.1	21.8	0.99	0.80	0.01
CD8+ CD57+%	22.7	35.1	0.01	0.38	0.31
CD8+ CD38+%	0.50	0.90	0.02	0.32	0.40
CD8+ DR+%	0.90	5.3	<0.001	0.67	<0.05
CD8+ CD69+%	0.55	1.00	0.44	0.59	0.10
CD8+ CD45RO+%	31.3	33.6	0.73	0.23	0.55

\*Represents the percentage of CD3+ T cells that expressed CD4 or CD8. All other values represent the percentage of CD4+ or CD8+ population expressing selected surface markers.

**2.2. Adipose resident CD8+ T cell density and TCR clonality is higher in obese mice fed a high-fat diet for 16 weeks compared to mice fed a low-fat diet.** To understand whether adipose-resident CD8+ T cell receptor oligoclonality varies with changes in adipose tissue, we assigned C57BL/6 mice to a chow, low-fat, or high-fat diet for 16 weeks (n=9 total) and then collected epididymal fat samples for T cell extraction, sorting, and T cell receptor surveillance

sequencing and clonality score calculation (a measure based on Shannon's entropy of the distribution of all TCR sequences – a higher clonality score indicates less entropy). Mice fed a high-fat diet were more obese and demonstrated the greatest number of CD8+ T cells per gram of adipose tissue (10,254 CD8+ cells/gram in high-fat; 9,940 cells/g in low-fat; and 3,922 cells/g in chow diet) and high-fat diet adipose tissue had greater expression of CD11b and F4/80 macrophage markers and IL-6 compared to low-fat diet ( $p<0.05$  for all). More striking, adipose-resident CD8+ T cell density was significantly correlated with T cell receptor clonality score ( $r=0.78$ ,  $p=0.01$ , **Table 2**), suggesting the increased CD8+ density in the obese mice represented an oligoclonal expansion.

**Table 2. Correlation between adipose-resident T cell density and clonality score in mice fed a chow, low-fat, or high-fat diet for 16 weeks (n=9)**

	Pearson's r	p-value
CD8+ cells	0.78	0.01
CD4+ cells	0.82	0.06

Density is calculated as the number of cells per gram of adipose tissue. CD4+ T cell recovery from chow mice was below the limit for sequencing (<1000 cells)

**2.3. Greater circulating CD4+ memory T cells are associated with the odds of incident diabetes in HIV+ persons on ART:** In pilot data from 76 male HIV+ Veterans Aging Cohort Study Biospecimen Cohort (VACS-BC) subjects, a higher proportion of memory T cells (CD4+ CD45RO+) was associated with a higher odds ratio for incident diabetes (OR= 10.0 for highest tertile of CD45RO+ cells versus lowest tertile; **Table 3**). There was also a positive relationship between TH1 cytokine producing cells and the odds of incident diabetes that was not statistically significant ( $p=0.16$ ), which may have been due to insufficient power. There were no significant findings for CD4+ or CD8+ T cell markers of activation or senescence. This finding, and similar results from the MESA cohort in non-HIV infected persons, supports our hypothesis that chronic immune activation of circulating T cells affects the insulin sensitivity of adipose and other metabolically active tissues.

**Table 3. Relationships of CD4+ memory cell and TH1 cell populations with incident diabetes in a pilot study of HIV+ VACS subjects**

CD4+ T cell subset	Odds ratio for incident diabetes	p-value
Memory (CD45RO+)	10.0	0.01
T H 1 (helper cell)	2.9	0.16

• Odds ratio for highest tertile of cells versus lowest tertile  
 • Logistic regression models adjusted for age, race, BMI, hepatitis C status, alcohol use, cocaine use, CD4 count, HIV-1 RNA, and CT visceral fat quantity.

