### 3.0 Hypotheses and Specific Aims

This study will assess the relationships of peripheral T cell distribution, adipose-resident T cell distribution, and adipose tissue inflammation in HIV-infected individuals, with the goal of understanding how chronic peripheral and tissue T cell activation may affect the risk of HIV-associated metabolic disease. If our hypotheses are correct, we will demonstrate that chronic peripheral immune activation (i.e., high memory T cells, low naïve cells, and increased expression of activation surface markers) is associated with greater adipose-resident CD4+ and CD8+ T cell expression of activation markers, the oligoclonal expansion of T cells expressing a restricted TCR repertoire, and adipose tissue inflammation.

**Aim 1:** To test the hypothesis that a higher percentage of activated CD4+ and CD8+ T cells in circulating blood is associated with a higher percentage of activated T cells in adipose tissue.

**Aim 2:** To test the hypothesis that activated T cells in adipose tissue contribute to macrophage activation, abnormal adipocyte gene expression, and glucose intolerance in HIV+ persons.

**Aim 3:** To test the hypothesis that adipose tissue from HIV+ patients with greater glucose intolerance is characterized by higher CD8+ T cell receptor oligoclonality, potentially reflecting an antigen-driven process.

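### Does the mouse pilot in section 2.2 overstate the link between obesity and CD8+ clonality in a way that affects the study?

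*Protocol*

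**What the plan says.** The heading of Protocol section 2.2 compares high-fat with low-fat mice and states that "TCR clonality is higher in obese mice fed a high-fat diet for 16 weeks compared to mice fed a low-fat diet", with CD8+ density named alongside clonality. The text gives the densities as "10,254 CD8+ cells/gram in high-fat; 9,940 cells/g in low-fat; and 3,922 cells/g in chow diet", without any measure of spread. The statement of p<0.05 directly follows the comparison of two macrophage markers and IL-6 between the high-fat and low-fat diets.

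The clonality score is described as "a measure based on Shannon's entropy of the distribution of all TCR sequences". The only clonality results are the correlations with density in Table 2, whose title covers all three diets and nine mice: r=0.78, p=0.01 for CD8+ and r=0.82, p=0.06 for CD4+. A note adds that too few CD4+ cells were recovered from chow mice to be sequenced. From the CD8+ correlation the text concludes, "suggesting the increased CD8+ density in the obese mice represented an oligoclonal expansion".

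Section 3.0 then sets out Aim 3: to test whether adipose tissue from HIV+ patients with greater glucose intolerance shows "higher CD8+ T cell receptor oligoclonality, potentially reflecting an antigen-driven process".

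**The concern.** The heading makes a two-group claim that the section does not document. On density the two groups are almost equal. On clonality there is no figure by diet at all. The correlation that stands in for it includes the chow mice, whose density is far below the other two groups, so it could arise from chow against the rest with nothing happening between high-fat and low-fat.

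A second worry is that an entropy-based score can depend on how many cells were sequenced, and that number is not given. A third is that the CD4+ row of Table 2 looks internally inconsistent.

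This is the only clonality evidence the protocol offers for Aim 3. A reader could take an obesity effect on clonality as already shown, and the rationale for Aim 3 would look firmer than it is.

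**Working it through.** Inputs, all from Protocol section 2.2: CD8+ densities of 10,254 (high-fat), 9,940 (low-fat) and 3,922 (chow) cells/g; nine mice in total; r=0.78, p=0.01 (CD8+); r=0.82, p=0.06 (CD4+). Mice per diet are not stated. Three per diet is assumed where a split is needed.

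**1. The stated CD8+ p-value.** t = r√((n−2)/(1−r²)) = 0.78 × √(7/0.3916) = 3.30 on 7 df, so p = 0.013. This rounds to the stated 0.01 and the row reproduces. The Fisher interval uses atanh(0.78) = 1.045 and SE = 1/√6 = 0.408, which gives a 95% CI for r of 0.24 to 0.95.

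**2. High-fat against low-fat density.**
- Difference: 10,254 − 9,940 = 314 cells/g, and 314/9,940 = 3.2%.
- Ratios to chow: 10,254/3,922 = 2.61 and 9,940/3,922 = 2.53.
- Share of the high-fat-to-chow gap already present in low-fat mice: 6,018/6,332 = 95%.
- Between-diet sum of squares, three mice each (overall mean 8,038.7): 3 × (2,215.3² + 1,901.3² + 4,116.7²) ≈ 76.4 million. The high-fat/low-fat part is 3 × 314²/2 = 147,894, or 0.19% (0.12% to 0.29% over all splits with at least two mice per diet).
- For 314 cells/g to reach p<0.05 with three mice per group, the within-diet SD would have to be below 314/(2.776 × √(2/3)) ≈ 139 cells/g, about 1.4% of the mean.

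**3. What the pooled correlation can tell.** Simulated sets of 3+3+3 mice were given identical clonality on the high-fat and low-fat diets and lower clonality on chow only. With chow 2.5 SD lower, the median r is 0.79, 0.72 and 0.65 at density CVs of 10%, 20% and 30%. With chow 3 SD lower, it is 0.77 at a CV of 20% and 0.68 at 30%. The shifts and CVs are assumptions. Illustrative group means with clonality lower on high-fat than low-fat (0.10 and 0.12, chow 0.05) still give r = 0.95. A pooled r near 0.78 therefore does not identify a high-fat/low-fat difference, although it does not contradict one.

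**4. The CD4+ row.** The same formula with r=0.82 gives p = 0.007 at n=9, 0.046 at n=6 and 0.089 at n=5. Rounding of r (0.815 to 0.825) gives 0.043 to 0.048 at n=6 and 0.086 to 0.093 at n=5. None of these is 0.06. An exact or permutation test could give another value, but none is mentioned. The nine in the title cannot apply to this row, as the table's own note makes plain.

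**5. Sequencing depth.** With assumed clone-size distributions, and cells per gram standing in for cells sequenced, a fixed repertoire sampled at 3,922 and then 10,254 cells gives a normalised score rising from 0.134 to 0.163 in one case and falling from 0.046 to 0.042 in another. Between 9,940 and 10,254 cells it moves by about 0.001 or less. The sign cannot be determined from the document, and the effect on the disputed contrast is negligible.

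**6. What the study takes from the pilot.** The group sizes of 96, 40 and 40 (section 4.1) are not derived from it. The glucose and HbA1c cutoffs separating the two non-diabetic groups (section 4.4) come from a diabetes guideline. The named primary outcome is two-hour glucose (section 4.5). Aim 3 (section 3.0) is a hypothesis in human tissue. No design quantity traces back to the mice.

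**The case for a change.** The best case for acting is that a protocol should not state a result its own figures do not show, above all when it is the sole clonality evidence for one of three aims. That is a statement on the page, not a detail that could be left to an analysis plan. The remedy is cheap: a narrower heading, clonality by diet if the data exist, and one corrected table row.

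Much of this stands as a comment on the text. The heading does go further than the data shown, and the CD4+ row contains a slip.

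Parts of it are weaker. Density is numerically higher in high-fat mice, so on density the fair word is similar rather than contradicted. The missing clonality scores are unreported, not in conflict with the claim, and the individual mouse data might support it. The 139 cells/g threshold tests a significance claim the protocol does not clearly make. Nor can the rise be called unrelated to adiposity, because no weights are given and low-fat mice may have been fatter than chow mice. The sequencing-depth argument does not stand, and the choice of clonality index for Aim 3 is analysis detail that may properly sit elsewhere.

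**Conclusion.** The observation is right in substance, but it calls for no change to the plan. High-fat and low-fat CD8+ densities differ by 3.2%, that contrast makes up about 0.19% of the between-diet variation, and r=0.78 pooled over three diets cannot show a clonality difference between those two groups. The CD4+ row is a clerical inconsistency in a non-significant result on which no claim rests.

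All of this sits in background rationale, where the inference is offered tentatively and the corresponding human hypothesis is left open for Aim 3 to test. If the pilot were misleading, the cost would be a weaker motivation for Aim 3, not a biased estimate or a wrong conclusion.

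The figures assume three mice per diet (the variation share stays between 0.12% and 0.29% under other splits) and the usual t test for a Pearson correlation. The conclusion also assumes that nothing outside the protocol takes a design value from these mice. An author revising the document for other reasons could tidy the heading and the table row.

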### 3.0 Hypotheses and Specific Aims

This study will assess the relationships of peripheral T cell distribution, adipose-resident T cell distribution, and adipose tissue inflammation in HIV-infected individuals, with the goal of understanding how chronic peripheral and tissue T cell activation may affect the risk of HIV-associated metabolic disease. If our hypotheses are correct, we will demonstrate that chronic peripheral immune activation (i.e., high memory T cells, low naïve cells, and increased expression of activation surface markers) is associated with greater adipose-resident CD4+ and CD8+ T cell expression of activation markers, the oligoclonal expansion of T cells expressing a restricted TCR repertoire, and adipose tissue inflammation.

**Aim 1:** To test the hypothesis that a higher percentage of activated CD4+ and CD8+ T cells in circulating blood is associated with a higher percentage of activated T cells in adipose tissue.

**Aim 2:** To test the hypothesis that activated T cells in adipose tissue contribute to macrophage activation, abnormal adipocyte gene expression, and glucose intolerance in HIV+ persons.

**Aim 3:** To test the hypothesis that adipose tissue from HIV+ patients with greater glucose intolerance is characterized by higher CD8+ T cell receptor oligoclonality, potentially reflecting an antigen-driven process.

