### 4.0 Study Methods

**4.1 Study Overview:** The study design incorporates a 3 year, two-visit longitudinal cohort study of 96 HIV+ subjects who are non-diabetic at enrollment but either at high risk (i.e., pre-diabetic) or lower risk (i.e., not pre-diabetic) of progressing to clinical diabetes, in addition to a cross-sectional study which will compare these non-diabetic HIV+ subjects to an additional 40 HIV+ diabetics and 40 HIV-negative diabetics (see **Figure**). The baseline and follow-up study visits will include fasting peripheral blood collection, glucose tolerance testing, CT quantification of adipose tissue, and subcutaneous abdominal adipose tissue biopsies using a liposuction cannula system to collect approximately 10 ml of tissue.

**4.2 Participant Recruitment:** HIV+ participants will be recruited from the Vanderbilt Comprehensive Care Clinic (VCCC), the largest HIV provider in central Tennessee and a principal study site for the AIDS Clinical Trials Group (ACTG). In 2014, a total of 2,954 HIV+ patients had at least one VCCC visit, including 358 new patients (up from 297 in 2013), and over 250 antiretroviral therapy-naïve adults start treatment yearly. Diabetic patients without HIV will be recruited from the Vanderbilt *ResearchMatch* cohort, an electronic clinical study volunteer registry. In March 2016 there were 180 adult volunteers with Type 2 diabetes mellitus within 50 miles of Vanderbilt University.

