**Figure: Subject groups, study design, and proposed assays**

Assays performed at each clinical visit :

- Clinical** → Glucose tolerance testing, CT fat quantification
- Adipose tissue** → Extracted T cells:
  - Flow cytometry & FACS sorting
  - CD4+ & CD8+ single T cell RNA expression profiling\*
  - CD4+ digital droplet latent HIV quantification (HIV+ only)
  - CD8+ T cell receptor sequencing\*
- Tissue** : Quantitative mRNA expression (macrophage activation and M1 vs. M2 phenotype cytokines, and adipocyte regulatory proteins)
- Peripheral blood** → T cell flow cytometry, CD4+ digital droplet latent HIV quantification (HIV+ only)

\*Single T cell RNA expression profiling and CD8+ T cell receptor sequencing will only be performed at the baseline visit. Cells will be stored from the follow-up visit.

potential racial, sex, and antiretroviral medication factors in our analysis.

As with the HIV+ subjects, we will aim to recruit roughly equal numbers of white and non-white participants, equal men and women, and an equal number of obese and non-obese HIV-negative subjects.

The enrollment schedule is shown in **Table 4**. We have estimated at least 80% of the HIV+ non-diabetic participants will be retained for the follow-up visit 3 years later ( $\geq 40$  per group) based on loss and refusal rates in VCCC ACTG longitudinal studies. Participants will be actively followed by the research nurse and asked to complete the second visit early if they plan to move out of the area or start on anti-diabetic medication.

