## 4.5 Study Procedures

**Blood collection:** We will collect 80 ml of fasting peripheral blood by percutaneous venipuncture on the left or right upper extremity. We will collect an additional 5 ml of blood at -15, 0, 30, 60, 90, and 120 min after ingestion of the oral glucose tolerance test (the 90 minute collection may be omitted if CT scan is performed during this time).

**Adipose tissue biopsy:** We will collect approximately 10 ml of subcutaneous adipose tissue (equivalent to roughly 9.5 g) using a specialized 2.7 mm blunt, side-ported peripheral liposuction catheter (Tulip CellFriendly™ GEMS system, Tulip Medical Products) designed for the efficient extraction of viable adipocytes and stromal vascular cells for outpatient cosmetic re-injection procedures. The GEMS system is ideal for our study due to the quantity of adipose tissue which can be obtained without injury to the cells. The procedure takes less than 15 minutes and blood loss is generally zero. This liposuction procedure is a standard technique for outpatient collection of subcutaneous adipose tissue and has been performed over 300 times at Vanderbilt.

**Oral glucose tolerance test:** All subjects will be fasting. We will draw blood at -15, 0, 30, 60, 90, and 120 min after oral administration of 75 g glucose syrup for measurement of serum glucose, insulin and C-peptide (the 90 minute collection may be omitted if CT scan is performed during this time). Glucose tolerance will be classified according to current American Diabetes

Association guidelines. Although the primary outcome will be two-hour glucose, we will calculate insulin sensitivity as the homeostasis model assessment (HOMA2) of insulin sensitivity ([www.dru.ox.ac.uk](http://www.dru.ox.ac.uk)). We will also calculate the Matsuda Index as  $10,000/\text{sqrt}(\text{Glucose}_0 \times \text{Insulin}_0 \times \text{mean glucose} \times \text{mean insulin})$  and the Insulinogenic Index defined as  $\Delta\text{Insulin} (0-30, \text{pmol/L})/\Delta\text{Glucose} (0-30, \text{mmol/L})$ .

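### Aim 1 looks for a positive blood-adipose association that residual blood in the aspirate would inflate, and the protocol names no measure of residual blood; the likely size depends on the marker

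*Protocol*

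**What the plan says.** Section 3.0, Aim 1, states a directional hypothesis: higher activation among circulating CD4+ and CD8+ T cells "is associated with a higher percentage of activated T cells in adipose tissue". Section 4.1 plans a "two-visit longitudinal cohort study of 96 HIV+ subjects" plus an "additional 40 HIV+ diabetics and 40 HIV-negative diabetics", with blood and a liposuction biopsy collected at each study visit.

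Blood contamination is mentioned once, for the ten-person pilot in section 2.1: "Adipose tissue biopsies were repeatedly washed to eliminate any blood contamination and T cells extracted". No check of the result is reported. The main-study biopsy paragraph in section 4.5 describes the cannula and the tissue volume, and adds "The procedure takes less than 15 minutes and blood loss is generally zero". It does not mention washing. The assay list under the Figure gives "Flow cytometry & FACS sorting" for T cells extracted from fat and names no red-cell, haemoglobin or other residual-blood reading.

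**The concern.** If a share c of the T cells recovered from an aspirate came from blood, the measured adipose percentage is c × blood + (1 − c) × tissue. The blood value then sits on both sides of the Aim 1 comparison and raises the correlation even when blood and tissue are unrelated. The bias runs the way the hypothesis predicts, so a positive result would not by itself tell the two explanations apart. Aims 2 and 3 also treat these cells as adipose-resident.

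The remark on blood loss reads as a statement about the participant, not about the blood content of the sample. An index that is not recorded when the aspirate is processed may not be recoverable later.

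**Working it through.** **The protocol's own figure first.** The protocol gives no contamination or power figure for Aim 1. The nearest is the pilot correlation for CD8+ DR+ (section 2.1, Table 1): rho 0.67, p<0.05, n=10. With t = r√((n−2)/(1−r²)) = 0.67 × √(8/0.551) = 2.55 on 8 df, p = 0.034. It reproduces.

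**Inputs from the protocol.** Blood CD4+ count above 350/µl (4.3, floor used); tissue 9.5 g (4.5); pilot adipose CD4+ : CD8+ = 34.0 : 60.9 (Table 1); mouse CD8+ density 3,922 to 10,254 cells/g (2.2).

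**Assumptions.** Human fat yields T cells at the mouse densities; residual blood is 20-50 µl; blood and tissue values are truly unrelated. None of these is in the protocol.

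**Step 1: share of recovered CD4+ cells that is blood.**
- Resident CD8+: 3,922 × 9.5 = 37,259, to 10,254 × 9.5 = 97,413.
- Resident CD4+ (× 34.0/60.9): 20,801 to 54,385.
- 20 µl carries 350 × 20 = 7,000 CD4+ cells: c = 7,000/61,385 = 11%, to 7,000/27,801 = 25%.
- 50 µl carries 17,500: c = 17,500/71,885 = 24%, to 17,500/38,301 = 46%.

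A CD4+ count above the floor raises these shares. A higher human yield lowers them.

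**Step 2: induced correlation.** With k = SD(blood)/SD(tissue), r = ck/√((1−c)² + (ck)²).
- Equal SDs (k = 1): c = 10/20/30% gives r = 0.11/0.24/0.39.
- Two-sided 5% critical r is 0.201 at n=96 and 0.168 at n=136 (96 + 40 HIV+ diabetics).

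**Step 3: let SD follow the median.** Take the true tissue median as (adipose − c × blood)/(1 − c) and k as the blood median over that value. At c = 20%:

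| Marker | Blood | Adipose | True tissue | k | Induced r |
|---|---|---|---|---|---|
| CD4+ CD38+ | 4.0 | 2.4 | 2.00 | 2.00 | 0.45 |
| CD4+ CD45RO+ (memory) | 50.3 | 57.4 | 59.2 | 0.85 | 0.21 |
| CD8+ CD38+ | 0.50 | 0.90 | 1.00 | 0.50 | 0.12 |
| CD8+ CD69+ | 0.55 | 1.00 | 1.11 | 0.49 | 0.12 |
| CD4+ DR+ | 1.0 | 2.5 | 2.88 | 0.35 | 0.09 |
| CD4+ CD69+ | 0.25 | 0.80 | 0.94 | 0.27 | 0.07 |
| CD8+ DR+ | 0.90 | 5.3 | 6.40 | 0.14 | 0.04 |

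Five of the six activation markers stay below both critical values. At c = 30% the two highest of these five (CD8+ CD38+, CD8+ CD69+) reach 0.20 and 0.19, about the critical values.

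**Step 4: compare with the pilot.**
- With equal SDs, c/(1−c) = r/√(1−r²). A rho of 0.83 needs c = 60%, and 0.95 needs 75%. In CD4+ terms that is about 88-231 µl and 181-473 µl of blood left after washing.
- CD4+ CD38+, the activation marker most exposed to carry-over, had rho 0.16. At c = 40% the model predicts 0.89; at 20% it predicts 0.45. An approximate 95% interval for 0.16 at n=10 is tanh(0.161 ± 1.96/√7) = −0.52 to 0.72. This speaks against 40% but not against 20%.
- CD8+ CD45RO+ (31.3 vs 33.6) had rho 0.23. At c = 20%, k = 0.92 and the predicted r is 0.22, so this row does not exclude moderate carry-over either.

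**The case against.** The strongest reply has three parts.

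**The protocol shows awareness of the problem.** The pilot washed repeatedly, and section 4.5 describes only clinical collection, with no digestion, staining or gating for any assay. Wash and quality-control detail may sit in a laboratory manual. This stands as far as it goes. A reader might infer that the main study drops the wash step, but silence in a collection paragraph does not show that. Even so, washing lowers contamination without measuring it, and nothing shown measures it.

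**Most Aim 1 markers are little exposed.** A reader might infer that a few tens of microlitres would create the Aim 1 correlation for activation markers in general. The pilot medians do not support that: five of the six are 1.8 to 5.9 times higher in fat than in blood. If spread follows level, 20% carry-over gives them at most 0.12. The equal-SD figure is therefore not representative of these five. Proportional SD is an assumption too, since the protocol reports no SDs.

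**The pilot does not look like contamination.** A reader might also infer that the pilot's correlations of 0.83-0.95 are carry-over. They would need 60-75% blood with equal SDs, above the 11-46% worked out here. The more than fivefold excess of CD8+ DR+ in fat also argues against near-total contamination. The low rho for CD4+ CD38+ and CD8+ CD45RO+ points the same way, but with about ten pairs it is weak evidence and leaves moderate carry-over open.

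**Conclusion.** The point holds in limited form. The direction of bias is certain under the mixing model and coincides with the Aim 1 hypothesis, and the protocol as shown provides no measurement that would separate the two explanations.

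The size is not known. It rests on an assumed residual volume, mouse cell densities standing in for human subcutaneous fat, and an assumed ratio of SDs. Within those assumptions, 20% carry-over could alone produce a significant association for CD4+ CD38+. For memory CD4+, which section 3.0 counts as part of peripheral immune activation, the induced value is about at the critical value for n=96 and above it for n=136. The five activation markers enriched in fat would be little affected at that level. The documents do not support the view that the pilot findings, or a future Aim 1 result as a whole, would be an artefact. This is a worthwhile, inexpensive improvement rather than a flaw that undermines the study.

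**What to change.** - In section 4.5, carry the pilot's wash step into the main-study procedure.
- Record one residual-blood index per aspirate from material already in hand, for example one granulocyte marker in the existing flow run, or haemoglobin in the final wash.
- Report the Aim 1 association as planned, with one sensitivity analysis that adjusts for the index or excludes aspirates with high values.

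A rule that counts Aim 1 as supported only when the association exceeds a modelled carry-over correlation is not advised. The modelled value depends on the SD ratio, which makes it too uncertain to serve as a threshold.

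The cost is one added marker or bench reading per aspirate and one extra analysis, with no additional visit or biopsy. The Aim 1 correlation may come out smaller.
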